7.2.3 Study Visit 1 – Baseline Testing and Initiation of the intervention

Study Visit 1 (Baseline measurements) will occur 0-30 days after the Screen 1 eligibility visit. The following procedures will be performed during this visit:

- 1) Review of medical history, medications, and laboratory test results
- 2) Symptom assessment and ECOG performance status
- 3) Vital signs assessment, including blood pressure, heart rate, and temperature; and measurement of height and weight
- 4) Blood collection for clinical labs (approximately 10 mL). Laboratory blood tests will be done for a Lipid Panel, hemoglobin A1C, and Creatine Phosphokinase (CPK) to establish baseline levels prior to initiating the study agent. CBDF and CMPL lab results from the Screen 1 eligibility visit will be used to establish patient-specific references prior to initiation of therapy. If blood tests were not done at the Screen 1 visit for a CBDF and CMPL; and lab results within 30 days prior to this visit for these tests are not available in the medical record, a CBDF and CMPL will be done at this visit. See Appendix E for Clinical Laboratory Minimum Test Requirements.
- 5) Blood collection for research (20 mL). Ten mL of blood will be collected for measurement of protocol-specific biomarkers (AFP, AFP-L3%, IL-6, and bile acids) and 10 mL of blood will be drawn for DNA extraction and use in future studies.
- 6) Liver elastography (FibroScan). A FibroScan examination will be conducted. Participants will be instructed to refrain from eating for 3 hours before the FibroScan examination. The FibroScan will be used as a non-invasive measurement of liver stiffness.
- Interviewer-administered baseline questionnaire to obtain demographic information (detailed race and ethnicity, education); medical and medications history; alcoholic beverage consumption; tobacco smoking; and anthropometry (Appendix F)
- 8) Food frequency questionnaire (FFQ). The VioScreen[®] graphical dietary assessment will be selfadministered to capture usual diet over the last 30 days.
- 9) Review of study requirements
- 10) Dispense the study agent (one bottle of 120 capsules) and review instructions for how to take it
- 11) Dispense and review the study diary

7.3 Evaluation During the Study Intervention

7.3.1 Study Visit 2

Study Visit 2 will occur 1 month (\pm 14 days) after initiation of the intervention. The following procedures will be performed during this visit:

- 1) Review of medical history, medications, and laboratory test results
- 2) Symptom assessment and ECOG performance status

- 3) Vital signs assessment, including blood pressure, heart rate, and temperature; and measurement of weight
- 4) Blood collection for clinical labs (approximately 10 mL). Laboratory blood tests will be done for a CBDF and CMPL to monitor for potential adverse effects of the intervention. If lab results within 30 days prior to this visit for CBDF or CMPL are available in the medical record, the blood test(s) will not be repeated. See Appendix E for Clinical Laboratory Minimum Test Requirements.
- 5) Review of study requirements
- 6) Collect study agent and diary
- 7) Assess compliance (pill count)
- 8) Review study diary
- 9) Assess adverse events
- 10) Dispense study agent (same bottle that was brought to the visit/collected for pill count) and diary

7.3.2 Study Visit 3

Study Visit 3 will occur 3 months (\pm 14 days) after initiation of the intervention. The following procedures will be performed during this visit:

- 1) Review of medical history, medications, and laboratory test results
- 2) Symptom assessment and ECOG performance status
- 3) Vital signs assessment including blood pressure, heart rate, and temperature; and measurement of weight
- 4) Blood collection for clinical labs (approximately 10 mL). Laboratory blood tests will be done for a CBDF, CMPL, Lipid Panel, and hemoglobin A1C to monitor for potential adverse effects of the intervention. If lab results within 30 days prior to this visit for any of these tests are available in the medical record, the blood test(s) will not be repeated. See Appendix E for Clinical Laboratory Minimum Test Requirements.
- 5) Review of study requirements
- 6) Collect study agent and diary
- 7) Assess compliance (pill count)
- 8) Review study diary
- 9) Assess adverse events
- 10) Dispense study agent (one new bottle of 120 capsules) and diary

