5.2 Study Agent Administration

Patients will self-administer the 40 mg capsule of simvastatin or placebo daily in the evening. Patients will be instructed to take the study agent at bedtime or with an evening meal. Each participant will be given/shipped one bottle of 120 capsules at Study Visit 1 (90-day supply + buffer) and one bottle of 120 capsules (90-day supply + buffer) at Study Visit 3 (Month 3).

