5.6 Dose Modification

No dose modifications are planned. The study agent will be stopped in the event of an AE \geq grade 3 considered possibly, probably, or definitely related to the study agent. The study agent will be restarted after resolution. One of the common side effects of statin medication is myalgia (muscle pain with normal Creatine Phosphokinase (CPK) level), and rarely this is associated with statin myopathy (muscle weakness or other muscle injury with or without elevation in CPK level). In randomized controlled trials of standard dose statin therapy, the risk is very low (<1%). We will measure levels of CPK in the blood drawn at the first study visit to establish a patient-specific reference for this indicator of muscle toxicity. During the trial, if the participant reports unexplained muscle pain or weakness, CPK will be tested again to check for elevation.

The study agent will be permanently discontinued in subjects experiencing grade 3 or greater myopathy (unexplained muscle symptoms *and* CPK > 5 times ULN) or hepatotoxicity (ALT or AST > 5 times

ULN) that is considered possibly, probably, or definitely related to the study agent. The study agent will be permanently discontinued in subjects experiencing the following grade 2 hepatotoxicities considered possibly, probably, or definitely related to the study agent: (1) hemorrhage requiring medical attention, and (2) symptomatic fistulas. All other grade 2 hepatotoxicities can be restarted after resolution.

Because dose modification could lead to lack of dose homogeneity that may impair the research objectives, we will stop the intervention in patients who initiate drugs that require dose modifications of simvastatin below 40 mg: lomitapide, verapamil, diltiazem, dronedarone, amiodarone, amlodipine, or ranolazine.

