7.6 Methods for Clinical Procedures

Blood specimen. A blood specimen (approximately 15 mL) will be collected from each participant at the Screen 1 eligibility visit for blood tests to confirm eligibility. If a patient's lab results are current (within the past 30 days) in the medical record and within eligibility range, their blood will not be drawn at the Screen 1 visit. Otherwise, the patient's blood will be drawn to confirm eligibility. Clinical labs will be done for a Complete Blood Count and Automated Differential (CBDF), a Comprehensive Metabolic Panel (CMPL), and Prothrombin Time (PT/INR). The CBDF includes tests for leukocytes, neutrophils, platelets, and hemoglobin; test results will be used to establish acceptable organ function necessary for trial eligibility. The CMPL includes tests for liver enzymes (AST/ALT); and for total bilirubin, creatinine, and sodium for calculation of the MELD score. Prothrombin Time is required for calculation of MELD. The CMPL and PT/INR test results will be used to confirm that blood levels are within the eligibility requirements (acceptable organ function, AST/ALT \leq 5x upper limits of normal, and MELD \leq 20).

A blood specimen (approximately 10-15 mL) will be collected from each participant at Study Visits 1, 2, 3, and 4 for blood tests to monitor for potential adverse effects of the intervention. The date and time of the blood draw and the participant's last meal will be recorded. A Lipid Panel and hemoglobin A1C will be done at Study Visits 1, 3, and 4. A CBDF and CMPL will be done at Study Visits 2, 3, and 4. Creatine Phosphokinase (CPK) will be measured at Study Visit 1. Prothrombin Time (PT/INR) will be done at Study Visit 4 to calculate the MELD score. See Appendix E for Clinical Laboratory Minimum Test Requirements.

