The CMPL and CBDF test results will be utilized to screen for any issues that could be related to an adverse event or affect eligibility for continuation in the trial. It is the consensus of the liver expert panel that obtaining baseline liver enzymes (AST/ALT) and monitoring them is optimal in the care of statin-treated patients [115]. CBDF and CMPL lab results from the Screen 1 eligibility visit (blood collected at most 30 days prior to Study Visit 1) will be used to establish patient-specific references prior to initiation of therapy. If blood tests were not done at the Screen 1 visit for a CBDF and CMPL; and lab results within 30 days prior to Study Visit 1 for these tests are not available in the medical record, a CBDF and CMPL will be done at Study Visit 1. The Lipid Panel includes tests for cholesterol, high density lipoprotein cholesterol, low density lipoprotein cholesterol, and triglycerides. Since the study agent is a cholesterol lowering agent, we feel that it is important to establish baseline lipid levels prior to initiating the study agent (Study Visit 1) and monitor lipids at Study Visits 3 and 4 (3- and 6-month visits). Hemoglobin A1C is used to assess glucose control in insulin-dependent diabetics whose glucose levels are very labile and in whom single blood glucose measurements may not accurately reflect the level of control present over the preceding few weeks. Glucose and hemoglobin A1C will be used for monitoring adverse events (incident diabetes) during the trial. CPK will be tested to establish a baseline for

monitoring myopathy, a rare complication associated with the study agent (<1%). We will measure levels of CPK at Study Visit 1 to establish a patient-specific reference for this indicator of muscle toxicity. If the participant reports unexplained muscle pain or weakness during the trial, CPK will be tested again to check for elevation.

An additional blood specimen (20 mL) will be collected from each participant at Study Visits 1 and 4 for research purposes. The blood will be drawn into one 10 mL red top serum vacutainer tube for measurement of protocol-specific biomarkers (AFP, AFP-L3%, IL-6, deoxycholic acid, and other serum bile acids and immune markers), and one 10 mL lavender top EDTA tube for DNA extraction and use in future studies.

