10. SPECIMEN MANAGEMENT

10.1 Laboratories

- Study blood tests will be done for a Complete Blood Count and Automated Differential (CBDF), a Comprehensive Metabolic Panel (CMPL), Prothrombin Time (PT/INR), a Lipid Panel, hemoglobin A1C, and Creatine Phosphokinase (CPK) at the clinical or local laboratories at each study site; or the blood tests will be done at an external CLIA-certified clinical laboratory as required by the participant's health insurance carrier.
- 2) At CSMC, specimen processing and aliquoting of blood samples collected for protocolspecific biomarker testing and for use in future studies will be performed by the CSMC Biobank & Translational Research Core Laboratory. Along with general supplies, the laboratory is fully equipped with the following instrumentation: Refrigerated Centrifuge, Ambient Centrifuge, -20°C Freezer, -80°C Freezer, 32°F Refrigerator, laboratory hood, water bath, Vortex Machine, calibrated pipettes, dry ice, and supplies. Freezers and refrigerators are on daily temperature monitoring and records are meticulously kept and stored for

documentation. These main instruments are also on red outlet plugs such that they trigger backup generator electricity in case of a black out. All instrumentation is calibrated prior to use and maintained yearly by the Biomedical Engineering Services department.

- 3) At NWU, specimen processing, aliquoting, and shipping of blood samples collected for protocol-specific biomarker testing and for use in future studies will be performed by Northwestern University Clinical and Translational Sciences Institute Clinical Research Unit and Core Lab. The lab is IATA, CAP and CLIA certified and has 570 square feet of space for both clinical and research specimen processing and analytical work (RIA; ELISA). The Core lab also has a 65 square-foot walk-in cold room for assay incubation and freezer storage at -30°C and -70°C. It accepts specimen submission 24 hours a day, 365 days a year, utilizes the "Freezerworks" bar code and inventory system and provides shipment of ambient and frozen research samples.

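### The month-1 safety panel at Study Visit 2 can be replaced by a blood sample drawn before the first dose

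*Combined protocol and SAP*

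**What the plan says.** Section 7.3.1 places Study Visit 2 one month (± 14 days) after the intervention starts. Item 4 gives the purpose of the laboratory work: "Laboratory blood tests will be done for a CBDF and CMPL to monitor for potential adverse effects of the intervention". It then adds a waiver: if results "within 30 days prior to this visit for CBDF or CMPL are available in the medical record, the blood test(s) will not be repeated". The waiver has no condition on when the sample was taken relative to the first dose.

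Other sections bear on this:

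- Section 7.2.3, item 4, covers participants with no CBDF/CMPL draw at Screen 1. If results from the 30 days before Visit 1 "are not available in the medical record, a CBDF and CMPL will be done at this visit". Visit 1 itself may be 0 to 30 days after Screen 1.
- Section 5.2: "Patients will self-administer the 40 mg capsule of simvastatin or placebo daily in the evening".
- Section 10.1 has these panels run "at the clinical or local laboratories at each study site", or at an external clinical laboratory, so their results can be in the medical record.
- Section 7.6 states the Visit 2 test without exception: "A CBDF and CMPL will be done at Study Visits 2, 3, and 4". It also says these results "will be utilized to screen for any issues that could be related to an adverse event or affect eligibility for continuation in the trial".
- Section 5.6 requires permanent discontinuation for drug-related "hepatotoxicity (ALT or AST > 5 times" ULN).

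**The concern.** A 30-day look-back from a visit at about 30 days can reach back to, or past, the start of treatment. A sample taken before any study drug cannot show an effect of the drug. Sections 7.2.3 and 7.6 also use the pre-treatment panel as the participant's own reference. If that same panel stands in for Visit 2, the change from reference is zero by construction.

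At stake is the first on-treatment check of liver enzymes and blood counts in people with cirrhosis who start directly on 40 mg. Section 4.1.4 admits AST/ALT up to 5 times ULN and Section 5.6 stops the drug above 5 times ULN, so a participant can start just under the limit. The four-weekly calls in Section 7.3.3 cover adherence, concomitant medication and symptoms. None of these would reveal a silent enzyme rise. CBDF and CMPL are the only clinical tests listed for Visit 2, so if both are waived no blood is drawn.

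**Working it through.** The plan gives no figure to reproduce. The check is day arithmetic, followed by an assumption-based estimate of how often the gap would apply.

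**Inputs.** Day 0 is Visit 1 and the first evening dose. Visit 2 is at 30 ± 14 days, so day v = 16 to 44 (7.3.1). The look-back is 30 days (7.3.1). The gap from Screen 1 to Visit 1 is 0 to 30 days (7.2.3). Visit 3 is at 90 ± 14 days, so days 76 to 104 (7.3.2). Visit 4 is at 180 ± 30 days, so day 150 at the earliest (7.4.1).

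**Which samples qualify.** The earliest admissible sample day is v − 30.

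- v = 16 gives day −14; v = 29 gives day −1; v = 30 gives day 0. A day-0 clinic sample would normally precede the evening dose.
- So 15 of the 29 window days (16 to 30) admit a sample from day 0 or earlier. Taking one month as 28 or 31 days makes this 17 or 14 of 29.
- A panel drawn g days before the first dose qualifies when v ≤ 30 − g, which is possible for g = 0 to 14.
- Visit 3: 76 − 30 = day 46. Visit 4: 150 − 30 = day 120. Both look-backs are always on treatment, so the gap is specific to Visit 2.

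**How often.** The documents give no timing distribution. The figures below are continuous approximations and assume that no later, on-treatment chart panel exists.

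*Fixed g, v uniform on 16 to 44:* probability = (14 − g)/28. This gives 50% for g = 0, 39% for g = 3, 25% for g = 7, 14% for g = 10 and 0% for g = 14 or more.

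*Scenario (a): every panel drawn at Screen 1, g uniform on 0 to 30.*

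- v uniform: (14²/2)/(30 × 28) = 98/840 = 0.117.
- v triangular on 16 to 44 with its peak at 30: (14³/6)/(196 × 30) = 457.3/5880 = 0.078.

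*Scenario (b): everyone enters on chart results aged a days at Screen 1, a uniform on 0 to 30, with the 7.2.3 redraw applied.* The redraw on day 0 happens when a + g > 30, probability 0.50. Half of those have Visit 2 by day 30, which contributes 0.50 × 0.50 = 0.25. The rest qualify when a + g + v ≤ 30.

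- v uniform: (14³/6)/(30 × 30 × 28) = 457.3/25,200 = 0.018; total 0.268.
- v triangular: (14⁴/12)/(2 × 900 × 196) = 3201.3/352,800 = 0.009; total 0.259.

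**In participants.** 0.078 × 80 = 6.2 and 0.268 × 80 = 21.4, so about 6 to 21 of 80. On simvastatin, 0.078 × 40 = 3.1 and 0.268 × 40 = 10.7, so about 3 to 11 of 40.

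**Delay.** The first assured on-treatment panel is the Visit 3 one, on days 76 to 104, or a chart result accepted in its place from day 46 at the earliest. Taking the course as 183 days, day 90 is 90/183 = 49% and day 104 is 104/183 = 57% of it.

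**Events.** Section 6.2 gives about 1% for persistent transaminase rises above 3 times ULN. 0.01 × 3.1 = 0.03 and 0.01 × 10.7 = 0.11 expected among the affected simvastatin participants.

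**The case against.** The strongest reply is that the waiver should be read with its purpose. The preceding sentence says the panel is for monitoring the intervention, pre-dose panels have their own role as references, and Section 7.6 and the schedule in Section 7.1 list both tests at Visit 2. A careful site would see the date of the panel and draw blood anyway. That supports what was intended, but the waiver is the visit-specific instruction and is worded as mandatory. No other section, including Appendix E, restricts it. A site that followed it exactly would skip the test.

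The reply is stronger on size. The frequency cannot be derived from the documents, and the upper figure assumes that everyone enters on chart results. Detection would be delayed rather than lost, because the panel is due again at Visit 3. The 1% rate is for rises above 3 times ULN over whole studies and is not stated to come from cirrhosis. It is therefore an imprecise guide to rises above 5 times ULN in the first months here. Section 6.2 recommends liver tests after initiation only when clinically indicated. The 57% figure is the latest-day case. All of this stands, and it makes this a modest safety gap. It does not remove the gap, because the protocol chose a scheduled month-1 test and this rule can cancel it.

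**Conclusion.** The concern holds. As written, a pre-dose panel can replace the Visit 2 CBDF/CMPL whenever Visit 2 falls on or before day 30 and such a panel lies within the look-back. That the rule allows this follows from the text alone. The size does not: 8% to 27% rests on the assumed timings, and the share is zero if every pre-dose panel is at least 15 days old at the first dose or every Visit 2 falls after day 30. The primary endpoint is untouched and few events would be expected. The change should still be made, because it restores a safety check that the same item orders and that Sections 5.6 and 7.6 rely on, at almost no cost.

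**What to change.** Amend Section 7.3.1, item 4, so that a record result replaces the Visit 2 CBDF or CMPL only if the sample was collected after the first dose; otherwise the test is drawn at Visit 2. A lower limit of day 16, the start of the Visit 2 window, would be preferable so that the result reflects some weeks of exposure. That limit is a judgement and does not come from the protocol. Sections 7.3.2 and 7.4.1 need no change.

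The cost is one sentence of wording and, under the assumptions above, a panel for about 6 to 21 of 80 participants at a visit where a draw of about 10 mL is already planned. With a day-16 limit the number would be somewhat higher, depending on how many have chart results from days 1 to 15, which the documents do not give. Sample size, endpoints and number of visits are unaffected.

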7.3.3 Telephone Calls and Email/Text Messages

Study participants will be followed during the intervention via telephone calls every four weeks (\pm 7 days) by the clinical research staff to assess compliance and adverse events. Participants who report having taken < 85% of the study drug doses between phone calls, or whose pill count at a study visit reveals < 85% compliance, will be called every two weeks (\pm 3 days) to monitor compliance. In addition, participants will receive a phone call the day before each scheduled study visit to remind them to bring any leftover study drugs and the study diary with them to the visit if it occurs in person. For remote visits patients will be called during the week before their final visit (Visit 4) to remind them to take the study drug every day until the visit appointment.

Participants who opt to receive reminders for study medication intake via email or text messages will be contacted by the study staff during the first week of study and further as needed. The study staff will send emails or text messages on cellular phone; participants will be encouraged to respond to these messages indicating if the study drug has been taken. These responses will be used to assess compliance and will be reviewed during phone contacts. For participants who miss more than one dose of the study drug in a week, the email/text reminders will continue further into dosing period. Since agent compliance is very important during the final week of the intervention, text/email messages will be sent to all study participants who opt to receive these reminders.

The following information with be collected during the telephone calls:

- Compliance review: participants will be asked if they missed any doses of the study medication, and the dates of all missed doses will be recorded.
- Concomitant medications review
- Adverse events: participants will be asked if they have experienced any of the following symptoms to assess adverse events:
 - Upper respiratory infection
 - Headache
 - Abdominal pain
 - Constipation
 - o Nausea
 - o Vomiting
 - Mild muscle aches
- Additional symptoms experienced by participants will be recorded to assess adverse events

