2.2 Study Agent

[figure not shown]

Figure 1. Molecular structure of simvastatin

Simvastatin (butanoic acid, see Figure 1) is a lipid-lowering agent that is derived synthetically from a fermentation product of *Aspergillus terreus*. After oral ingestion, simvastatin, which is an inactive lactone, is hydrolyzed to the corresponding β -hydroxyacid form. This is an inhibitor of 3-hydroxy-3-methylglutaryl-coenzyme A (HMG-CoA) reductase. This enzyme catalyzes the conversion of HMG-CoA to mevalonate, an early and rate-limiting step in the biosynthesis of cholesterol. The empirical formula of simvastatin is C₂₅H₃₈O₅ and its molecular weight is 418.57. Simvastatin is a white to off-white, nonhygroscopic, crystalline powder that is practically insoluble in water, and freely soluble in chloroform, methanol, and ethanol.

Simvastatin tablets for oral administration contain 5 mg, 10 mg, 20 mg, 40 mg, or 80 mg simvastatin and the following inactive ingredients: ascorbic acid, citric acid, hydroxypropyl cellulose, hypromellose, iron oxides, lactose, magnesium stearate, microcrystalline cellulose, starch, talc, and titanium dioxide. Butylated hydroxyanisole is added as a preservative.

Simvastatin is the most commonly prescribed HMG-CoA reductase inhibitor, which has a widely accepted tolerability profile with few serious side effects [21]. Potential, but uncommon side effects include muscle, liver, and kidney problems. Elevated levels of creatine kinase and rhabdomyolysis occur in <1% of consumers, and myalgia, or muscle ache or weakness, can occur in approximately 5% of consumers [22]. In a clinical trial database in which 41,413 patients were treated with simvastatin, 60% of whom were enrolled in studies with a median follow-up of at least 4 years, the incidence of myopathy was approximately 0.03% and 0.08% at 20 and 40 mg/day, respectively. The incidence of myopathy with 80 mg (0.61%) was disproportionately higher than that observed at the lower doses [23].

Simvastatin is prescribed for primary and secondary prevention of cardiovascular disease and thus is indicated for long-term use. We propose to administer simvastatin 40 mg daily for 6 months in this trial.

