6.2 Reported Adverse Events and Potential Risks

The most common reported adverse events (incidence $\geq 5.0\%$) are upper respiratory infection, headache, abdominal pain, constipation, and nausea. Other adverse events reported in clinical trials (<5%) were diarrhea, rash, dyspepsia, flatulence, and asthenia.

Persistent increases in serum transaminases (to more than $3 \times$ the ULN) have occurred in approximately 1% of patients who received simvastatin in clinical studies. When drug treatment was interrupted or discontinued in these patients, the transaminase levels usually fell slowly to pretreatment levels. The increases were not associated with jaundice or other clinical signs or symptoms. It is recommended that liver function tests be performed before the initiation of treatment, and thereafter when clinically indicated.

Simvastatin occasionally causes myopathy manifested as muscle pain, tenderness, or weakness with creatine kinase above ten times the ULN. Myopathy sometimes takes the form of rhabdomyolysis with or without acute renal failure secondary to myoglobinuria, and rare fatalities have occurred. The risk of myopathy is increased by high levels of statin activity in plasma. Predisposing factors for myopathy include advanced age (≥65 years), female gender, uncontrolled hypothyroidism, and renal impairment. The risk of myopathy, including rhabdomyolysis, is dose related. The risk of myopathy and rhabdomyolysis is increased by high levels of statin activity in plasma. Simvastatin is metabolized by the cytochrome P450 isoform 3A4 (CYP3A4). Certain drugs which inhibit this metabolic pathway can raise the plasma levels of simvastatin and may increase the risk of myopathy. These include itraconazole, ketoconazole, posaconazole, voriconazole, the macrolide antibiotics erythromycin and clarithromycin, the ketolide antibiotic telithromycin, HIV protease inhibitors, boceprevir, telaprevir, the antidepressant nefazodone, cobicistat-containing products, or grapefruit-containing products. Combination of these drugs with simvastatin is contraindicated. If short-term treatment with strong CYP3A4 inhibitors is unavoidable, therapy with simvastatin must be suspended during the course of treatment.

Increases in HbA1c and fasting serum glucose levels have been reported with HMG-CoA reductase inhibitors, including simvastatin.

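### The only route to an on-treatment CPK is a participant's report of muscle pain or weakness, yet neither the printed call list nor the diary examples name weakness

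*Combined protocol and SAP*

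**What the plan says.** Sections 7.1 and 7.6 and Appendix E schedule one CPK measurement: "Creatine Phosphokinase (CPK) will be measured at Study Visit 1", the baseline visit at which the agent is first dispensed. After that, section 5.6 provides that "if the participant reports unexplained muscle pain or weakness, CPK will be tested again to check for elevation"; section 7.6 and Appendix E say the same, and no other route to an on-treatment CPK is given. Section 5.6 then requires permanent discontinuation for related myopathy of grade 3 or higher, which it defines by muscle symptoms together with CPK above 5 times ULN.

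Two printed tools prompt participants between visits. On the calls made every four weeks (7.3.3), "participants will be asked if they have experienced any of the following symptoms to assess adverse events"; the list has seven entries, and the single muscle entry is "Mild muscle aches". The Appendix C diary gives examples of side effects to write down (headache, gut complaints, respiratory infection, rash), none of them a muscle symptom. Both tools also accept any other symptom.

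Section 6.2 describes the hazard: "Simvastatin occasionally causes myopathy manifested as muscle pain, tenderness, or weakness with creatine kinase above ten times the ULN".

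**The concern.** The myopathy rule runs in sequence: a report leads to a CPK, and the CPK decides the permanent stop. Asking is the first step, so the questions should use the words of the trigger. Section 5.6 says pain or weakness, and section 6.2 says pain, tenderness or weakness. The call list asks about mild aching, and the diary examples ask about no muscle symptom at all.

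A participant with new weakness but no ache can truthfully answer no to the muscle item at every call. Someone with cirrhosis may put weakness down to the liver disease and not raise it. If so, CPK is not repeated and dosing continues until the symptom surfaces some other way. The stake is participant safety, not the efficacy result.

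**Working it through.** The plan states no figure to reproduce. The check sets trigger and prompts side by side and then asks what the documents allow one to say about size.

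**1. Scheduled CPK (7.1, 7.6, Appendix E).** Visit 1 only: 1 of 4 study visits, and 0 of the 3 on-treatment visits (Visits 2, 3 and 4).

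**2. Prompts against trigger.** Nausea and vomiting are counted separately in both tools.

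| Symptom | CPK trigger (5.6) | Call list (7.3.3) | Diary examples (App. C) |
|---|---|---|---|
| Muscle ache or pain | yes | 1 of 7, worded as mild | 0 of 7 |
| Weakness | yes | 0 of 7 | 0 of 7 |
| Open item for other symptoms | n/a | yes | yes |

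Ache is partly covered: a yes to mild aches can be taken as reported muscle pain and so lead to a CPK under 5.6. The unmatched element is weakness.

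**3. Time between visits.** Four-weekly calls fall nominally on days 28, 56, 84, 112, 140 and 168, which is 6 calls. The longest interval between visits is Visit 3 to Visit 4: nominally 3 months (about 91 days), and with Visit 3 up to 14 days early and Visit 4 up to 30 days late, 91 + 14 + 30 = 135 days. During that time the calls and diary are the scheduled safety contacts. Physical assessment is listed only at Screen 1 and Visit 4.

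**4. Size.** Section 2.2 gives rates for general users, not for cirrhosis. Applied to the 40 participants on simvastatin:
- Ache or weakness combined ("myalgia, or muscle ache or weakness, can occur in approximately 5% of consumers"): 0.05 × 40 = 2.0 expected; chance of at least one, 1 − 0.95^40 = 0.87.
- Myopathy ("the incidence of myopathy was approximately 0.03% and 0.08% at 20 and 40 mg/day, respectively"): 0.0008 × 40 = 0.032 expected; chance of at least one, 1 − 0.9992^40 = 0.03.

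The first figure is a ceiling, not the number missed. If f is the share of those complaints that are weakness without ache and are not volunteered through any open route, the number missed is 2.0 × f. The documents do not give f. It lies between 0 and 1 and is probably near the low end, because ache is already prompted and the open routes exist.

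**The case against.** The case against is substantial, and most of it stands.

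- **Open routes exist.** Calls record additional symptoms, and the diary invites any other symptom. Visits include an interval symptom history, ECOG status and, on treatment, adverse event review. Section 5.4 tells participants to call the study doctor about a serious reaction. This stands: no reporting channel is missing.
- **Severe cases have another stop.** Section 5.6 also stops the agent for any related event of grade 3 or higher, with no CPK needed, and grade 3 includes limitation of self-care (11.1.3). This stands, although that stop allows restart after resolution and still needs the event to come to light.
- **The list has a rationale.** Its entries follow the commonest reported events in section 6.2, with vomiting and muscle aches added. This is true, but a list of common events is not matched to a rule that depends on a particular symptom.
- **Some material is not visible.** The consent form, adverse event form and any working call script may ask more. The point is therefore limited to the prompts printed in 7.3.3 and Appendix C.

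A reader might go further in three ways that the documents do not support. One is that about 2 participants would be missed; that figure counts ache, which the calls already ask about. Another is that weakness would go unnoticed until the next visit; that requires every intervening call's open item, the diary and the participant's own initiative all to fail. The third is that bleeding needs a prompt too, because section 5.6 makes "hemorrhage requiring medical attention, and (2) symptomatic fistulas" permanent stops. That rule covers related grade 2 events, and a bleed that needed medical attention can be reached through the history, medication and laboratory review at each visit. A bleeding prompt would also draw in background events in a population with varices and platelets down to 50,000 per microliter.

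**Conclusion.** The mismatch is confirmed on the text: weakness is half of the stated CPK trigger and a named sign of myopathy, and no printed prompt mentions it. The consequence is limited to sensitivity and timeliness for weakness not volunteered between visits. The number affected cannot be derived from the documents and is probably small; full myopathy is expected in about 0.03 participants at the general-user rate, and no rate for cirrhosis is given.

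The prompts are the same in both blinded arms, so the wording introduces no bias between arms, and the AFP-L3% endpoint is untouched. This is a cheap safety improvement at the low end of what should be changed, not an error in the design. It does not support adding scheduled CPK tests: a symptom-driven CPK is a coherent choice, provided that the symptoms are asked about.

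**What to change.** In section 7.3.3, replace the mild-aches item with *unexplained muscle aches, pain or weakness*, and add the same phrase to the Appendix C examples. Keep both open items, the CPK schedule and the section 5.6 rules unchanged. Add no bleeding or black-stools prompt. A neutral question on any emergency or hospital visit since the last contact is optional. When attributing a new muscle complaint, compare it with the Visit 1 questionnaire items on muscle cramps and decreased strength (Appendix F), which are already collected.

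Costs:
- A protocol amendment with DCP and CIRB approval (14.3), and Spanish re-translation of the changed participant materials (4.4).
- Staff time: almost none for the reworded item. The optional question, at an assumed 1 minute (range 0.5 to 2) over 6 × 80 = 480 on-treatment calls, takes 8 hours (4 to 16) across the trial.
- CPK re-tests: if an assumed 5% to 20% of the 80 participants report a muscle complaint, 0.05 × 80 = 4 to 0.20 × 80 = 16 tests in total, assuming one each. The extra number is smaller, since some would be tested under the present wording.
- Slightly more background muscle complaints in both arms, which could dilute the binary toxicity comparison in section 13.7 a little.
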